Clinical investigation plan

C17-614 (EX-MKTG-85)

**A fitting evaluation of hydrogel and silicone hydrogel
spherical contact lenses**

**A clinical evaluation for
CooperVision Inc.**

Study Leader

Principal Investigator

May 2017

Contents

[figure not shown]
Document control	3
Study summary	
Section 1. Overview	5
1.1 Background	5
1.2 Personnel	5
1.3 Study objectives	5
1.4 Study design	5
1.5 Statistical considerations	5
1.6 Risk analysis	6
Section 2. Resources	7
2.1 Subject selection	7
2.2 Subject discontinuation	8
2.3 Safety parameters, adverse events and concurrent illnesses	8
2.4 Study termination	9
2.5 Protocol deviations	9
2.6 Study resources	9
2.7 Study control	10
2.8 Documentation	10
2.9 Data collection and analysis	10
2.10 Study completion	11
2.11 Confidentiality	11
2.12 Study monitoring	11
Section 3. Subject management	12
3.1 Visit scheduling	12
3.2 Visit conduct	12
3.3 Monitoring subject compliance	17
3.4 Missing, unused and spurious data	17
Section 4. Study co-ordination	18
4.1 Document processing	18
4.2 Disclosure	18
4.3 Personnel	18
Appendices	
A Adverse events	
B Randomisation table	
C Grading scales, questionnaires	

Document control

Study title: A fitting evaluation of hydrogel and silicone hydrogel contact lenses (C17-614) (EX-MKTG-85)

Sponsor company: CooperVision Inc.

Document type: Clinical investigation plan.

Study summary

This double-masked, randomised, bilateral crossover non-dispensing study will compare the clinical performance and subjective acceptance of the NewDay, Biomedics 1-day and Proclear 1-day daily disposable soft contact lenses.

Forty subjects will be enrolled on this study and will wear each lens type for approximately one hour on three separate study days in random sequence. The following will be assessed throughout the study: ocular physiology, lens fit, visual acuity, and subjective response.

A study summary is shown in Table 1.

Visit	Procedures
Information and consent presentation Visit 1	Short on-line presentation of study aims and procedures Informed consent taken Explanation of study procedures and subject instructions Medical, ocular and contact lens history Refraction Auto-keratometry Biomicroscopy Fitting of lens pair 1 Visual acuity Subjective scores Lens fit
Visit 2	Subjective scores Visual acuity Lens fit Biomicroscopy
Visit 3	Medical and ocular history Biomicroscopy Fitting of study lens pair 2 Visual acuity Subjective scores Lens fit
Visit 4	Subjective scores Visual acuity Lens fit Biomicroscopy
Visit 5	Medical and ocular history Biomicroscopy Fitting of study lens pair 3 Visual acuity Subjective scores Lens fit
Visit 6	Subjective scores Visual acuity Lens fit Biomicroscopy Exit form signed and payment issued

Table 1: Study summary.

Section 1. Overview

1.1 Background

This project seeks to compare the short-term clinical performance of the NewDay, Biomedics 1-day and Proclear 1-day (all CooperVision Inc.) daily disposable soft contact lenses.

1.3 Study objectives

This study aims to compare the short-term clinical performance of the three contact lenses.

1.4 Study design

This will be a randomised, double-masked, crossover, bilateral non-dispensing study, controlled by cross-comparison. Forty subjects will wear each lens brand for approximately one hour, on three separate study days in random order. Lenses will only be worn during study visits.

1.5 Statistical considerations

The principal hypothesis to be tested in this work is that high contrast visual acuity in the lenses will be substantially equivalent.

Visual acuity assessment, biomicroscopy, lens surface data and subjective responses will generate data that are likely to be continuous and normally distributed. As such, these will be compared using linear regression models or other parametric methods. Subjective preferences will be compared using chi-squared tests. Lens fit data are expected to be ordinal data and assessed with non-parametric approaches. Deviations from this statistical plan will be discussed in the final report. Deviations may be necessary due to differences between the actual data distribution compared with the anticipated data distribution.

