1.5.1 Power analysis

Assessment using a dataset from a similar, previous study found that a power of 0.89 or greater is provided by 35 completing subjects to detect a 0.05 difference in high contrast visual acuity. This analysis assumes a two-tailed paired analysis and an alpha of 0.05. To allow for discontinuations, 40 subjects will be recruited.

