Signs	Conjunctival redness Limbal redness Corneal neovascularisation Epithelial microcysts Corneal oedema Corneal staining Location of staining Conjunctival staining Conjunctival indentation Papillary conjunctivitis	Blepharitis Meibomian gland dysfunction Mucin balls
Scale	Efron Grading Scales (scored to nearest 0.1)	Efron Grading Scales (scored to nearest 0.1) (except mucin balls, where the number is recorded.

Table 3: Biomicroscopic signs.

The presence of any ocular adverse events will be recorded (see Appendix A).

5. The investigator will confirm that the subject satisfies all the inclusion and exclusion criteria. Subjects who fail to meet all the criteria at this time will usually be discontinued and replaced.
6. The first randomised lens pair (Appendix B) will be fitted and allowed to settle for five minutes. Subjects will insert the study lenses themselves.

7. Monocular logMAR visual acuity (high contrast) will be recorded before performing an over-refraction, and then monocular and binocular logMAR visual acuity (high contrast only) will be carried out with the over-refraction in place, and in accordance with the current Eurolens Research Standard Operating Procedure 'Assessment of visual performance using the Bailey-Lovie logMAR visual acuity test chart and procedures for carrying out an over-refraction'.
8. If an over-refraction of $\pm 0.50D$ or more is found, a second lens pair will be applied and Step 7 above will be repeated.
9. The subject will be asked to score the following with reference to appropriate visual analogue scales (0-100) (Appendix C):
 - Handling
 - Comfort
 - Burning/stinging
 - Distance vision

11. Lens fit will be assessed using the following evaluations: horizontal and vertical centration, corneal coverage and movement. Normally, for an acceptable fit, centration and movement will fall within currently accepted clinical criteria [between 1 and +1 on a -2 to +2 grading scale (Appendix C)]. If the lens is graded as 'unacceptable' (i.e. any of the grades are +2 or -2), the investigator should state why.

12. Lens tightness on push-up will be recorded using the grading scale in Appendix C.

14. The subject will be asked to return after the study lenses have been in situ for one hour.

3.2.3 Visit 2

After approximately one hour of lens wear, the subject will return to the clinic and the following assessments will be made:

1. Recording of any ocular symptoms, adverse events since lens application.

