2. The subject will be asked to score the following scores with reference to appropriate visual analogue scales (0-100) (Appendix C):
 - Comfort
 - Burning/stinging
 - Distance vision
2. Monocular logMAR visual acuity (high contrast) will be recorded before performing an over-refraction, and then monocular and binocular logMAR visual acuity (high contrast only) will be carried out with the over-refraction in place, and in accordance with the current Eurolens Research Standard Operating Procedure 'Assessment of visual performance using the Bailey-Lovie logMAR visual acuity test chart and procedures for carrying out an over-refraction'.

15. Lens fit will be assessed using the following evaluations: horizontal and vertical centration, corneal coverage and movement. Normally, for an acceptable fit, centration and movement will fall within currently accepted clinical criteria [between 1 and +1 on a -2 to +2 grading scale (Appendix C)]. If the lens is graded as 'unacceptable' (i.e. any of the grades are +2 or -2), the investigator should state the reasons why.

4. Lens tightness on push-up will be recorded using the grading scale in Appendix C.

6. The subject will remove the lenses and will be asked to score the following with reference to appropriate visual analogue scales (0-100) (Appendix C):

- Handling on removal

7. Slit lamp biomicroscopy will be performed as described in Section 3.2.2.

8. Subjects will be discharged and asked to attend the next study day without their habitual lenses in situ.

3.2.4 Visit 3

Subjects should attend this visit without their contact lenses in situ. The following will be carried out:

1. Recording of any ocular symptoms, adverse events and concomitant medications since the last visit.
2. Monocular logMAR visual acuity (high contrast) in each eye using the refraction result found in Section 3.2.2 in accordance with the current Eurolens Research Standard Operating Procedure 'Assessment of visual performance using the Bailey-Lovie logMAR visual acuity test chart and procedures for carrying out an over-refraction'.
3. Slit lamp biomicroscopy will be carried out for the signs outlined in Table 4 and in accordance with the current Eurolens Research Standard Operating Procedure 'Examination of the anterior segment using slit lamp biomicroscopy'. Grades will be scored to the nearest 0.1 unit in the best judgement of the investigator using Efron Grading Scales.

Classification	Primary signs	Secondary signs

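### The principal hypothesis is equivalence of high contrast acuity, but the plan sets no margin or decision rule, and its power of 0.89 is for detecting a difference

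*Combined protocol and SAP*

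**What the plan says.** Section 1.5 names one principal hypothesis: "The principal hypothesis to be tested in this work is that high contrast visual acuity in the lenses will be substantially equivalent". For acuity, together with biomicroscopy, lens surface and subjective data, the only method given is that "these will be compared using linear regression models or other parametric methods".

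Section 1.5.1 justifies the sample size by stating that "a power of 0.89 or greater is provided by 35 completing subjects to detect a 0.05 difference in high contrast visual acuity", and adds: "This analysis assumes a two-tailed paired analysis and an alpha of 0.05". Forty subjects are recruited to allow for dropout. The section gives neither the SD nor the unit of the 0.05; acuity is recorded in logMAR elsewhere. The 0.05 is nowhere called a margin.

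Acuity is measured in several ways, at fitting and again after one hour (Sections 3.2.2 and 3.2.3). "Monocular logMAR visual acuity (high contrast) will be recorded before performing an over-refraction"; after that, "monocular and binocular logMAR visual acuity (high contrast only) will be carried out with the over-refraction in place". No measure or visit is named as primary.

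**The concern.** The hypothesis and the power statement point in opposite directions. In the test described in Section 1.5.1, a significant result is evidence of a difference, and a non-significant result is only an absence of evidence. Neither outcome establishes equivalence. A regression would give confidence intervals for the lens differences, but there is no margin to judge them against.

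The study could therefore finish with complete data and no pre-stated basis for its main conclusion, and any margin would be chosen after the results were known. The plan does not say that non-significance would be read as equivalence. If it were, the risk of a false claim would depend on the SD and the number of completers, and would not be held at a stated level.

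**Working it through.** **Inputs.** From Section 1.5.1: n = 35 completers, difference δ = 0.05 (taken as logMAR), two-sided alpha 0.05, paired analysis, power 0.89 or more. From Section 1.4: three lenses, hence three pairwise comparisons. Not given: the SD of paired differences and an equivalence margin. Both are assumptions below.

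**1. The plan's own figure.** Paired t-test power is P(T > t₀.₉₇₅,₃₄), with T noncentral t on 34 df and noncentrality δ√n/SD. Solving for power 0.89 gives SD = 0.0902:

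- standard error = 0.0902/√35 = 0.0152
- noncentrality = 0.05/0.01524 = 3.28
- critical value = 2.032

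The stated power is plausible for a difference test, but it cannot be verified without the SD. Because the text says 0.89 or greater, 0.0902 is the largest SD consistent with it. SDs of 0.08 and 0.07 would give power of 0.949 and 0.984.

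**2. Non-significance read as equivalence.** The chance of p > 0.05 when the true difference is 0.05 is 1 − power. The comparison is two one-sided tests (TOST) with margin ±0.05, each at one-sided 0.05.

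| SD | n = 35 | n = 30 | TOST, either n |
|---|---|---|---|
| 0.0902 | 11.0% | 16.5% | 5.0% |
| 0.08 | 5.1% | 8.9% | 5.0% |
| 0.07 | 1.6% | 3.4% | 5.0% |

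**3. How often the two rules disagree.** Simulated for one pair at a true difference of 0.02 with n = 35:

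| SD | Non-significant, equivalence not shown | Significant, equivalence shown |
|---|---|---|
| 0.0902 | 16% | 1.5% |
| 0.08 | 6% | 6% |
| 0.07 | 1% | 18% |

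The direction depends on the SD. No single SD in this range gives large disagreement both ways.

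**4. Power of the equivalence test.** A pair passes if |mean difference| + t₀.₉₅,ₙ₋₁ × SE < margin. As a rough check at SD 0.0902, n = 35 and zero true difference: the 90% CI half-width is 1.691 × 0.01524 = 0.0258, leaving 0.05 − 0.0258 = 0.0242, or 1.59 standard errors. Then 2Φ(1.59) − 1 ≈ 0.89. Integrating over the sample variance gives 0.883. Results at margin ±0.05, except the ±0.04 row:

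| Case | SD 0.0902 | SD 0.08 | SD 0.07 |
|---|---|---|---|
| One pair, n = 35, true difference 0 | 0.883 | 0.952 | 0.987 |
| One pair, n = 35, true difference 0.01 | 0.809 | 0.892 | 0.952 |
| One pair, n = 35, true difference 0.02 | 0.610 | 0.701 | 0.799 |
| One pair, n = 35, true difference 0, margin ±0.04 | 0.646 | 0.790 | 0.905 |
| All three pairs, n = 35, true difference 0 | 0.74 | 0.88 | 0.97 |
| All three pairs, n = 40, true difference 0 | 0.83 | 0.94 | 0.99 |

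The all-pairs rows are simulated with equal variances and correlations. If a 95% CI is used instead of a 90% CI, one-pair power at SD 0.0902, n = 35 and zero true difference is 0.78.

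**The case against.** The best defence is that the harm is conditional and the numbers are modest. The plan never says that it would take non-significance as equivalence. Section 1.5.1 already supplies 0.05 as the difference of interest, so a regression CI could be read against it, and one-pair power hardly changes (0.88 against 0.89). If the SD is 0.08 or less, the naive error with 35 completers is already about 5% or lower. Section 1.3 asks only for a comparison of short-term performance, and the lenses are CE marked and worn for about an hour in clinic.

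Most of this is true, and it limits the size of the problem. It does not supply the missing rule. A reader would have to guess that 0.05 is the margin, which confidence level applies, which pairs must pass and which acuity measure is meant. A low error rate that depends on an unstated SD is not a controlled one.

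Two objections to the remedy stand. A 90% CI is not the only valid choice: a 95% CI is stricter and costs power. Nor is it certain that 40 subjects suffice, because that depends on the margin, the pairs required and the true differences.

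**Conclusion.** The concern holds. The plan's only principal hypothesis is one of equivalence, with no margin and no rule for concluding it, and 0.89 is power for a different question. The gap is mainly in the definition of the test. With a ±0.05 margin, a 90% CI, one pair and zero true difference, 35 completers give 0.88 at the largest SD consistent with Section 1.5.1.

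The shortfall becomes material at that SD if all three pairs must pass (0.74), if the true difference is 0.02 (0.61), if the margin is ±0.04 (0.65) or if a 95% CI is used (0.78). It is smaller at lower SDs. All these figures rest on a back-solved SD and on borrowing 0.05 as a logMAR margin. The absence of a margin and rule rests on neither. It should be corrected before the data are analysed.

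**What to change.** **In Section 1.5:**

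- Test the principal hypothesis with two one-sided tests. Declare a lens pair equivalent only if the 90% CI for the mean paired difference lies wholly inside a pre-stated margin that the sponsor justifies. ±0.05 logMAR is the natural candidate. If the sponsor prefers a 95% CI, say so and power for it.
- State that a non-significant difference is not evidence of equivalence.
- Name the lens pairs that must pass. If all three must pass, no alpha adjustment is needed.
- Name one primary acuity measure and visit. Binocular acuity is recorded only with the over-refraction in place, which may mask differences between lenses. Monocular acuity before over-refraction reflects the lenses alone but carries residual refractive error. Section 3.2.2 provides for one exchange, at ±0.50D ("or more is found, a second lens pair will be applied and Step 7 above will be repeated"), and mentions no further exchange, so that error is normally, but not certainly, below 0.50D. A monocular measure also needs a stated method for handling the two eyes.

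**In Section 1.5.1:** restate power for this test, giving the SD of the chosen measure from the previous dataset, at zero and at small non-zero true differences.

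**Cost:** wording, a justified margin and possibly a less favourable power figure. Data collection does not change. The sample size need not change for a single pair at ±0.05. If the sponsor requires all three pairs or a tighter margin, it should check that the restated power at 35 to 40 completers is acceptable.

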3.2 Visit conduct

3.2.1 Pre-enrolment

The subject will receive a study-specific information form outlining the study at least 24 hours before the initial visit

At a suitable time, each subject will be asked to watch a short on-line information presentation detailing study visits and procedures. They will be asked to complete several multiple-choice questions to gauge their understanding of the study. Upon successful completion of these questions, the subject will be booked to attend the initial visit. Subjects should be asked not to wear their habitual contact lenses on the day of the study visit.

3.2.2 Visit 1

Subjects should attend this visit wearing their spectacles. They will then be required to sign an informed consent form prior to enrolment. A copy of the signed form will be issued to the subject. When the subject has signed the consent form, they are considered to be enrolled on the study.

Subjects will be instructed on the following:

1. Lens handling, application and removal, where necessary.

2. Specific study instructions, such as the importance of not using any other contact lens products.
3. General contact lens information such as the management of red eyes.

The following procedures will be performed (any ocular measurement procedures outlined below will be carried out on each eye):

1. Details of the ocular history and contact lens wearing history of the subject will be noted (including habitual lenses, modality, wear time and comfortable wear time).
2. Auto-keratometry measures will be recorded.
3. The investigator will perform refraction and distance monocular logMAR visual acuity (both high and low contrast), in accordance with the current Eurolens Research Standard Operating Procedure 'The set up, measurement of visual acuity and procedures for carrying out an over refraction using the Eurolens computerised logMAR VA chart'.
4. Slit lamp biomicroscopy will be carried out for the signs outlined in Table 4 and in accordance with the current Eurolens Research Standard Operating Procedure 'Examination of the anterior segment using slit lamp biomicroscopy'. Grades will be scored to the nearest 0.1 unit in the best judgement of the investigator using Efron Grading Scales.

Classification	Primary signs	Secondary signs

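### Section 1.5 sends all biomicroscopy to a parametric analysis for continuous normal data, although the sign list includes a location and a count, and it gives the same-day pre-lens grade no role

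*Combined protocol and SAP*

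**What the plan says.** Section 1.5 (Statistical considerations) handles biomicroscopy as one block. Together with acuity, lens surface measurements and subjective scores, it "will generate data that are likely to be continuous and normally distributed". It continues: "As such, these will be compared using linear regression models or other parametric methods". Only lens fit is treated differently: "Lens fit data are expected to be ordinal data and assessed with non-parametric approaches". A closing clause allows for change: "Deviations may be necessary due to differences between the actual data distribution compared with the anticipated data distribution". Any such change is to be discussed in the final report. No trigger and no replacement method is named.

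The signs are listed in Table 3 (section 3.2.2, Visit 1) and again in Table 4 (section 3.2.4, Visit 3). For most of them, "Grades will be scored to the nearest 0.1 unit in the best judgement of the investigator using Efron Grading Scales". Two entries differ in kind. Location of staining stands among the primary signs. Mucin balls stand among the secondary signs and are exempt from grading: "except mucin balls, where the number is recorded".

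The slit lamp is used twice on each lens day. It is used before fitting at Visits 1, 3 and 5, and after lens removal at Visits 2, 4 and 6. Visit 2, step 7 reads: "Slit lamp biomicroscopy will be performed as described in Section 3.2.2". Section 1.5 does not mention the pre-lens grade.

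**The concern.** A linear model needs a numerical outcome. A staining location is a label, so a mean difference in it between lenses has no meaning. A count of mucin balls is numerical, but it is not the continuous normal variable that section 1.5 describes.

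The graded signs raise a milder question. Subjects with abnormalities that contraindicate lens wear are excluded, and each lens is worn for about an hour. Some signs, such as microcysts or oedema, may therefore be absent in most subjects. A paired interval then rests on a few non-zero differences and can miss a real lens difference more often than its nominal 5%.

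The open deviation clause leaves the replacement method to be chosen after the data are seen. The pre-lens grade, which could remove day-to-day variation at no extra visit cost, has no stated use. What is at stake is the secondary comparison of ocular physiology.

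**Working it through.** **The plan's own figure.** The only statistical figure is in section 1.5.1: power of at least 0.89 with 35 completers for a 0.05 difference in acuity, two-tailed, paired, alpha 0.05. It does not concern biomicroscopy. No SD is given, so it cannot be reproduced. Solving the paired t power for 0.89 gives an implied SD of differences of about 0.090 logMAR. This bears on nothing below.

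**Data type against method.** This needs no arithmetic. Location is nominal, mucin balls are a count, and section 1.5 gives neither a separate method.

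**Interval checked for the grades.** Mean difference ± t(0.975, n−1) × s/√n, with n = 35 and 20,000 simulated trials per setting. The available text gives neither the scale limits nor the expected share of zero grades. All prevalences, limits, SDs and correlations below are therefore assumptions, shown over a range.

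*Model 1.* The sign is present independently on each lens, with non-zero grades from 0.3 to 1.5 (mean 0.9).

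| Present, lens v lens | True mean difference | Coverage |
|---|---|---|
| 2% v 2% | 0 | 0.997 |
| 2% v 6% | 0.9 × 0.04 = 0.036 | 0.863 |
| 2% v 10% | 0.9 × 0.08 = 0.072 | 0.910 |
| 5% v 15% | 0.9 × 0.10 = 0.090 | 0.939 |
| 5% v 20% | 0.9 × 0.15 = 0.135 | 0.945 |

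At 2% v 6%, 13.4% of intervals lie wholly below the true increase and 0.3% wholly above it. At 2% v 2%, every difference is zero with probability (0.98²)^35 = 0.243. The resulting zero-width interval contains the true value, which is zero.

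*Model 2.* Latent normal, SD 0.5, within-subject correlation 0.5, floored at 0, capped at 4, rounded to 0.1.

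| Share of zeros | Coverage, n = 35 | Coverage, n = 40 |
|---|---|---|
| 40% v 50% | 0.950 | 0.950 |
| 60% v 80% | 0.940 | 0.943 |
| 80% v 90% | 0.918 | 0.926 |
| 80% v 95% | 0.896 | 0.899 |
| 90% v 98% | 0.822 | 0.833 |

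With equal lenses and n = 35, coverage is 0.950 to 0.963 for 30% to 80% zeros. For 90% to 98% zeros it is 0.979 or higher among trials with any variation. No variation at all occurs in 0.6% (90% zeros), 8% (95%) and 36% (98%) of trials.

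*Counts.* Gamma-Poisson with a shared subject effect, n = 35. Equal means of 1 or 0.2 give 0.955 to 0.961. Unequal means give 0.925 (0.5 v 0.2), 0.900 (2 v 1, highly dispersed) and 0.877 (0.2 v 0.05).

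**Would rank or exact methods repair this?** Under Model 1, the interval matching a signed-rank test has zero width in 99.5% of trials at 2% v 6% (t interval: 6%), 77% at 5% v 15% and 48% at 5% v 20%. Exact McNemar rejects in 0.7% to 0.8% of trials at 2% v 6% (t: 4.5%) and 8% at 2% v 10% (t: 19%). The reason is plain. Expected discordant pairs at 2% v 6% are 35 × (0.02 × 0.94 + 0.06 × 0.98) = 2.7. A two-sided exact paired test needs at least six, all in one direction, to reach 0.05 (2 × 0.5^6 = 0.031; with five, 0.0625).

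**Covariate or change score.** Let r be the within-subject, same-day correlation of pre- and post-wear grades, with equal variances. Relative to ignoring the pre-lens grade, residual variance is 2(1 − r) for a change score and 1 − r² for a covariate. The change score is worse than no adjustment when r < 0.5. The covariate is never worse, apart from one degree of freedom. The documents do not give r, so the gain cannot be sized.

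**The case against.** A reader might infer that the plan forces ordinary regression on every sign. It does not. The text says *likely*, permits other parametric methods (a Poisson-type model for mucin balls would qualify), and anticipates that the data may look different. It also promises no confidence interval for any sign, so under-coverage describes a natural output of the named method rather than a stated deliverable.

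The floor is inferred, not documented. Subjects are current or recent soft-lens wearers, and nothing shows that conjunctival or limbal redness would sit at zero. Where coverage falls below about 0.92 for a graded sign, the true mean differences are under 0.1 grade, the scoring step. Silence about the pre-lens grade does not exclude its use.

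Most of this stands, and it limits the point. Three things survive. No parametric method makes a location code interpretable. The deviation clause names neither trigger nor replacement, so the choice follows sight of the data. A baseline collected on three days should have a stated role.

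**Conclusion.** The point holds as a specification gap for secondary measures. The mismatch for location and mucin balls, and the missing role for the pre-lens grade, are plain from the text and need no assumption. The interval problem is conditional. Coverage of about 0.82 to 0.92 arises for rarely present signs (in Model 2, about 80% or more zeros) when the lenses also differ, with misses mostly understating the difference. Sparse or highly dispersed counts with unequal means behave similarly. Elsewhere, coverage is near or above nominal.

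Two stronger readings are tempting, and neither is supported. The first is that the plan yields wrong intervals for the signs that matter for safety. Section 2.3 makes the serious and significant events of Appendix A the key safety parameters. Those defined by grade thresholds are recorded as events, not as mean grades, so no safety conclusion rests on these intervals. The principal hypothesis concerns acuity and is unaffected. The second is that the 24% of zero-width intervals at 2% v 2% is a coverage failure. Those intervals are uninformative, but they contain the truth.

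**What to change.** Replace the biomicroscopy rule in section 1.5 with a rule by type of sign:

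- **Graded signs:** compare post-wear grades between lenses within subject, with the same-day pre-lens grade as a covariate and not as a mandatory change score. Use a within-subject permutation of lens labels, keeping each day's pre- and post-wear grades together, as the reference test.
- **Rarely present signs:** fix in advance the number of subjects below which a sign counts as rare. Report the number with an increase on each lens, with an exact paired comparison, and acknowledge its low power. The six-pair minimum shown above is a useful guide to the cut-off.
- **Mucin balls:** analyse as presence or with a count model, and choose which in advance.
- **Location of staining:** tabulate only.

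A signed-rank interval should not be adopted as the remedy, because it collapses to zero width for the very signs at issue. Acuity can stay in the linear model.

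The cost is wording in section 1.5, slightly more programming and some loss of power for rare signs. No visit, procedure or sample size changes.

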Signs	Conjunctival redness Limbal redness Corneal neovascularisation Epithelial microcysts Corneal oedema Corneal staining Location of staining Conjunctival staining Conjunctival indentation Papillary conjunctivitis	Blepharitis Meibomian gland dysfunction Mucin balls
Scale	Efron Grading Scales (scored to nearest 0.1)	Efron Grading Scales (scored to nearest 0.1) (except mucin balls, where the number is recorded).

Table 4: Biomicroscopic signs.

The presence of any ocular adverse events will be recorded (see Appendix A).

4. The second randomised lens pair (Appendix B) will be fitted and allowed to settle for five minutes. Subjects will insert the study lenses themselves.
5. Steps 7-14 in Section 3.2.2 will be repeated.

3.2.5 Visit 4

After approximately one hour of lens wear, the same procedures as Visit 2 will be performed.

3.2.6 Visit 5

Subjects should attend this visit without their contact lenses in situ. The same procedures as Visit 3 will be performed, with the third lens pair being applied.

3.2.7 Visit 6

After approximately one hour of lens wear, the same procedures as Visit 2 will be performed.

At the final visit (or when the subject is discontinued at an earlier visit) the subject will sign a study exit statement acknowledging that the work is complete, although they may have been asked by the investigator to attend a post-study follow-up visit, and that they should continue to use their lenses and solutions as advised, and seek aftercare for their contact lenses. A copy of this signed form will be issued to the subject.

The subject will be issued with their payment and discharged.

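### Section 1.5 gives the same-day pre-lens acuity and slit-lamp readings no stated role, so precision may be lost in the acuity and slit-lamp lens comparisons

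*Combined protocol and SAP*

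**What the plan says.** **Pre-lens readings.** At Visit 1 (section 3.2.2), refraction and monocular acuity are step 3 and slit lamp is step 4; the first lens pair is fitted at step 6. At Visit 3 (section 3.2.4), step 2 is "Monocular logMAR visual acuity (high contrast) in each eye using the refraction result found in Section 3.2.2", step 3 is slit lamp, and fitting follows at step 4. For Visit 5, section 3.2.6 says: "The same procedures as Visit 3 will be performed, with the third lens pair being applied". Each lens day therefore has its own pre-lens acuity and slit-lamp grades.

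**Later readings.** High contrast acuity in the lenses is measured after settling and again at about one hour, each time before and with over-refraction. After lens removal, section 3.2.3 step 7 states: "Slit lamp biomicroscopy will be performed as described in Section 3.2.2". Visits 4 and 6 repeat Visit 2.

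**Analysis.** For acuity, biomicroscopy, lens surface data and subjective responses, section 1.5 says: "As such, these will be compared using linear regression models or other parametric methods". It names no outcome time point, covariate, or subject, period or eye term.

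**Power.** Section 1.5.1 claims "a power of 0.89 or greater is provided by 35 completing subjects to detect a 0.05 difference in high contrast visual acuity", and adds: "This analysis assumes a two-tailed paired analysis and an alpha of 0.05". It gives no standard deviation and no baseline term.

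**The concern.** Pairing within subject removes what is stable about a person. It does not remove what differs from one lens day to the next, and section 3.1 puts those days at least 24 hours apart. The same-day pre-lens reading is the trial's direct measure of that variation for acuity and for the slit-lamp signs, and it is already being collected. If it is left out, day-to-day variation stays in the error of each acuity and slit-lamp contrast. The principal hypothesis is that acuity in the lenses is substantially equivalent, and such a claim rests on narrow intervals.

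The silence also leaves a choice open. The wording of 1.5 allows no adjustment, a change from the pre-lens reading, or covariate adjustment. As shown below, these can differ materially in precision. Section 1.5 justifies deviations by the distribution of the data, and the choice of covariate is not a question of distribution.

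**Working it through.** **Inputs from section 1.5.1:** n = 35 completers, difference 0.05 (taken as logMAR; the unit is not stated), two-sided alpha 0.05, paired, power 0.89.

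**Not in the documents:** the standard deviation (SD) of paired differences, and rho. Here rho is the correlation between the lens-to-lens difference in the pre-lens reading and the lens-to-lens difference in the outcome, that is, the within-subject correlation. It is assumed to lie between 0 and 0.7.

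**Step 1: the plan's figure.** The stated power cannot be reproduced independently, because the SD is attributed only to a previous dataset. Solving for the SD that yields 0.89:
- Normal approximation: 0.05 × √35 / (1.960 + 1.227) = 0.0928.
- Noncentral t, 34 df: 0.0902, a standardised difference of 0.05/0.0902 = 0.554.

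The second value is used below. Entering it returns 0.89 by construction, so this is not a check of the plan's claim.

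**Step 2: covariate adjustment.** The variance relative to the unadjusted contrast is (1 − rho²) × 33/32. The factor (n − 2)/(n − 3) = 33/32 is the cost of estimating the slope. Power uses the noncentral t with 33 df and SD = 0.0902 × √(relative variance). Equivalent unadjusted subjects are 35 divided by the relative variance.

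**Step 3: change score.** The relative variance is 2(1 − rho), assuming equal variances before and after, with 34 df.

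| rho | Covariate: relative variance | Equivalent unadjusted subjects | Covariate: power | Change score: relative variance | Change score: power |
|---|---|---|---|---|---|
| 0 | 1.03 | 34 | 0.88 | 2.0 | 0.62 |
| 0.3 | 0.94 | 37 | 0.91 | 1.4 | 0.77 |
| 0.5 | 0.77 | 45 | 0.95 | 1.0 | 0.89 |
| 0.7 | 0.53 | 67 | 0.99 | 0.6 | 0.98 |

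Unadjusted power is 0.89 in every row.

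**Step 4: break-even.** Covariate adjustment equals no adjustment when (1 − rho²) × 33/32 = 1, so rho² = 1/33 and rho = 0.17. The change score breaks even when 2(1 − rho) = 1, so rho = 0.5.

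**Step 5: dependence on the SD.** With other assumed SDs, unadjusted power at n = 35 is 0.998 (SD 0.06), 0.949 (0.08), 0.820 (0.10) and 0.668 (0.12).

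**Step 6: consistency of the acuity covariate.** For the pre-lens acuity, Visit 1 cites the procedure for the computerised logMAR chart. Visit 3, and Visit 5 by reference, cite the Bailey-Lovie chart procedure and reuse the Visit 1 refraction. Table 1 lists acuity at Visits 3 and 5 only after fitting, whereas section 3.2.4 takes it before fitting as well.

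**The case against.** The strongest case for the plan is that an unadjusted paired comparison is valid in a randomised crossover, matches the stated power basis, and already has a claimed power of 0.89. Nothing in the documents shows that rho reaches 0.5, and below about 0.17 adjustment loses a little precision. All of this stands. It limits the size of the point but does not explain why readings taken on every lens day have no stated use.

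It can also be objected that the acuity covariate mixes two chart procedures. This stands in part. A period term absorbs a constant shift between Visit 1 and the later days, but not a difference in measurement error. The slit-lamp grades are not affected.

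A reader might infer more than the documents support:

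- **That the plan excludes the pre-lens readings.** It does not. Section 1.5 is silent, and a linear regression can carry a baseline covariate.
- **That every lens comparison is affected.** Comfort, burning/stinging, distance vision, handling and lens fit have no pre-lens reading on the same scale, and preferences cannot have one.
- **That signs already present, such as blepharitis or neovascularisation, are mistaken for lens effects.** Each subject wears all three lenses, so stable signs cancel within subject; only day-to-day fluctuation remains.
- **That the comparison is biased or that carry-over is being missed.** Lens order is randomised, so fluctuation is noise. No carry-over is shown after about an hour of wear with at least 24 hours between days, and adjusting for one noisy reading would not in general remove it.

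**Conclusion.** The point holds as a gap in specification with a possible loss of precision, confined to high contrast acuity and the slit-lamp signs.

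On the back-solved SD, adjustment moves power at 35 completers from 0.89 to between about 0.88 (rho 0) and 0.99 (rho 0.7). The gain is about 2 points at rho 0.3 and 6 at rho 0.5. The worst case is about 3% more variance, at rho 0.

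These figures rest on an SD inferred from the plan's own power, on an assumed rho, and on a single pair of lenses with one acuity value per subject and lens. They illustrate the acuity endpoint. For slit-lamp grades the same relative variances apply at a given rho, but the documents give no basis for a power figure.

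The change is worth making before data are seen, because the readings are already collected and the possible gain is larger than the possible loss.

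**What to change.** **In section 1.5,** state that in-lens high contrast acuity and each slit-lamp sign will be analysed in a model with lens, period, subject and eye terms, with the same-day, same-eye pre-lens reading as covariate. For acuity this is the refraction-corrected pre-lens value; for a sign it is the pre-lens grade. Split the covariate into the subject's mean over the three days and that day's deviation from it, so that the lens contrast is adjusted by the within-subject relation only. State that a change score will not be used, because it has more variance than no adjustment when rho is below 0.5. Name the in-lens acuity reading that is the outcome.

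**In section 3.2 and Table 1,** reconcile the two acuity procedures cited for the pre-lens readings, and align Table 1 with the pre-fitting acuity at Visits 3 and 5. Keep the period term in any case.

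**Cost:** a short addition to 1.5 and two editorial corrections. It needs no new data or visits and uses one or two degrees of freedom, with about 3% more variance if rho is 0. If the previous dataset behind 1.5.1 holds comparable pre-lens readings, rho can be estimated from it beforehand and reported with the SD.
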